be assessed for symptoms of UTI since surgery by assessment of: urethral discomfort, suprapubic tenderness or pelvic pain, sense of urinary urgency, frequency or dysuria, fever, antibiotic use, and clinical and laboratory data suggesting infection (UA with +leukocyte esterase +/- nitrates, urine culture with $>10^5$ bacterial colony forming units per mL (CFU)). Asymptomatic bacteriuria will be considered a UTI for this study (defined as $>10^5$ CFU/mL on urine culture). Patients who are treated with antibiotics for UTI without laboratory data suggesting infection will be included in UTI group. For participants reporting ED visits prior to 14 +/- 2 day visit, ED reports will be obtained and an assessment will be made regarding the symptomatic UTI diagnosis. Those meeting these criteria will be followed with symptom and laboratory analysis. All positive UA test will be confirmed by laboratory analysis for final diagnosis. Results of +leukocyte esterase +/- nitrites will be considered abnormal. If a diagnosis of UTI does not exist in the patient chart outside of study, the patient's clinical picture will be evaluated independently by 2 separate care providers to determine if meeting criteria for UTI (symptomatic bacteriuria as defined above). If there is discrepancy a third provider will be the determining opinion. Participants meeting the primary endpoint (UTI) will be discontinued from the study following.

Secondary outcomes include: hospital length of stay, readmissions, antibiotic use at the time of surgery and post-surgery. Measures of UTI, and secondary outcomes will be collected from observation during study visits and from the patient medical charts., If closed drainage system was disrupted during placement (to back fill bladder intra-operatively), and method of catheter discontinuation ("fill and pull" versus "pull and void" methods) will be collected for comparison between the groups for analysis as a possible confounding variables.

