- Consent and randomization: Patients will be randomized to standard of care intraoperative catheter placement versus aseptic protocol for catheter insertion upon providing informed consent. Randomization will be performed using the REDCap randomization module and will be performed by the study coordinator or research manager.
- Urine analysis with urine dip: Patients will be asked to provide a clean catch urine sample in provided collection cup prior to surgery (done as standard of care), a catheter collected urine sample at 24hrs post-operatively (research procedure) and another clean catch specimen at their 2-week surgical follow-up (research procedure). This collection and analysis is low risk except for the possibility of unnecessary treatment if abnormal sample is obtained. Abnormal samples will be correlated with patient history/complaints and confirmed with formal urine analysis. Confirmation of UTI would also utilize urine culture. The urine analysis by dip gives a fast yet reliable indicator of urinary tract infections. Pre-operative/pre-randomization allows us to exclude patients who may have underlying UTI prior to initiation of the study.
- Catheter placement: The aseptic protocol involves dipping standard catheter in an aseptic betadine solution and leaving a pre-existing plastic cover in place over the catheter during insertion and while in place. We do not anticipate any added risk of the aseptic protocol to the patient although patients may experience some increased irritation due to the protective plastic cover.

Anticipated Risks

While the study anticipates minimal risks, the following outlines any potential minimum risk to subjects:

- i. **Breach of Confidentiality:** Data obtained using information from medical records poses minimal risk. All procedures in which information is being obtained will be conducted per standard of care. There is a risk that a patient's privacy may not be protected. This risk is uncommon.

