- ii. **Discomforts:** Persons receiving catheter insertion can anticipate the following risks: primarily ascending infection of the urinary tract. This usually presents initially with symptoms such as pain with urination, urinary urgency, urinary frequency, abdominal pain, chills, and/or fever. As discussed above the number of patients with evidence of clinical (symptomatic) and subclinical (asymptomatic) UTI has been reported to be as high as 40%. Other risks of catheter placement include urinary leakage around the catheter and bladder spasm/irritation while the catheter is in place. These symptoms usually resolve when the catheter is removed. Uncommon risks include injury to the bladder or urethra, urethral narrowing or urinary stone formation. Patients in both arms will be monitored for these risks throughout the study period. The addition of Betadine on the catheter prior to insertion is not expected to pose an increase in the described risks or discomforts.

Participation in this study will not have any influence on the patient's current treatment. The study may include risks that are unknown at this time.

Event reporting

Adverse Events

An Adverse Event [AE] is defined as any unfavorable and unintended sign (including abnormal laboratory finding), symptom, or disease temporally associated with the use of a medical treatment or procedure, regardless of whether it is considered related to the medical treatment or procedure (attribution of unrelated, unlikely, possible, probable or definite). An unanticipated event is defined as any adverse experience where the nature, severity or frequency is not identified in the investigational brochure described in the application form or detailed in the consent form. This can also include non-compliance issues such as over enrollment of subjects without prior COMIRB approval.

Investigators will report the following to COMIRB within 5 days:

- Adverse events which in the opinion of the principal investigator are both unexpected and probably or definitely related to the intervention/ drug or device.
- **Probably related:** In the opinion of the PI, it is more likely than not that the adverse event is related to the study intervention.
- **Definitely related:** In the opinion of the PI, it is very likely that the adverse event is related to the study intervention
- An unforeseen development that potentially increases the likelihood of harm to participants or others in the future.

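### Antibiotic treatment without laboratory evidence counts as a primary event, and the plan describes no arm-masked review of those cases

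*Combined protocol and SAP*

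**What the plan says.** Section IV.a (Performance Measurement) gives several routes to the primary endpoint.

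- **Culture.** "Asymptomatic bacteriuria will be considered a UTI for this study", at the plan's threshold of more than 10^5 CFU/mL.
- **Positive urine analysis.** "All positive UA test will be confirmed by laboratory analysis for final diagnosis".
- **Treatment alone.** "Patients who are treated with antibiotics for UTI without laboratory data suggesting infection will be included in UTI group". The sentence sets no symptom, culture or review condition.
- **Provider review.** It begins "If a diagnosis of UTI does not exist in the patient chart outside of study". The clinical picture is then "evaluated independently by 2 separate care providers to determine if meeting criteria for UTI (symptomatic bacteriuria as defined above"). A third provider settles disagreement.
- **Emergency department visits.** Reports are obtained and the symptomatic diagnosis is assessed. The assessor is not named.

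The same section describes supporting evidence as "clinical and laboratory data suggesting infection (UA with +leukocyte esterase +/- nitrates, urine culture with" more than 10^5 CFU/mL, so a dipstick positive for leukocyte esterase is itself laboratory data suggesting infection.

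On knowledge of the arm, section IV.c has the operating physician insert the catheter and the operation note document the insertion. Section IV.e keeps the plastic cover on while the catheter is in place in the aseptic arm. No section describes masking of patients, prescribers, assessors or reviewers. Post-surgery antibiotic use is also a separate secondary outcome.

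**The concern.** A decision to prescribe is enough to make a primary event, and the plan's checks do not reach it. A woman treated for UTI by her clinicians will ordinarily have a charted diagnosis, which bypasses the two-provider review. If she did reach review, she would fail its criterion for lack of laboratory evidence. The rule would count her and the review would not.

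Two consequences follow. If antibiotic-only events are equally common in both arms, they dilute the effect and cost power. If they differ by arm because clinicians know who had the aseptic catheter, the trial can detect a difference in prescribing and report it as a difference in infection. Section V itself warns that attention to a protocol may give a false impression of improvement.

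A separate gap concerns the study dipstick. Section IV.e accepts that its urine testing is "low risk except for the possibility of unnecessary treatment if abnormal sample is obtained". Section IV.a does not say how to classify a woman treated on a positive dip whose laboratory confirmation is negative.

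**Working it through.** **Inputs from the documents.** Control rate 40%, a 50% reduction (so 20%), 100 per arm, alpha 0.05, power 0.84 (section IV.b); 1:1 allocation (section IV.c); Bonferroni adjustment for two time points, so 0.025 per test (section VI). A two-sided test is assumed because sidedness is not stated.

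**Input not in the documents.** f, the share of women without true UTI who are counted only because they were treated. All values of f are assumptions.

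**Step 1: reproduce the plan's figure.** The continuity-corrected power is Φ[(d − 1/n − 1.96·SE0)/SE1], with d the difference in rates and n = 100.

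- SE0 = √(2 × 0.30 × 0.70/100) = 0.0648
- SE1 = √(0.40 × 0.60/100 + 0.20 × 0.80/100) = 0.0632
- Power = Φ[(0.20 − 0.01 − 1.96 × 0.0648)/0.0632] = 0.840

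This matches the stated 0.84, so the sample size is not in error on its own terms.

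**Step 2: equal f in both arms.** Observed rate = p + (1 − p)f. For f = 10%: 0.40 + 0.60 × 0.10 = 0.46 and 0.20 + 0.80 × 0.10 = 0.28.

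| f | Observed rates | Relative reduction | Continuity-corrected power |
|---|---|---|---|
| 0 | 40% vs 20% | 50% | 0.840 |
| 5% | 43% vs 24% | 44% | 0.774 |
| 10% | 46% vs 28% | 39% | 0.705 |
| 15% | 49% vs 32% | 35% | 0.637 |

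This adds treated-only cases to the planning rate. Section IV.e describes the 40% as symptomatic plus asymptomatic UTI and does not mention treated-only cases. If the 40% already included them, dilution would remain. With f = 5%, the true control rate is (0.40 − 0.05)/(1 − 0.05) = 0.368, half of it is 0.184, and the observed aseptic rate is 0.184 + 0.816 × 0.05 = 0.225. Power without continuity correction is then 0.765, against 0.876 for 40% vs 20%.

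**Step 3: unequal f, no true effect, true rate 30% in both arms.** The same formula gives the observed rates. For f = 10% vs 5%: 0.30 + 0.70 × 0.10 = 0.370 and 0.30 + 0.70 × 0.05 = 0.335. Rejection probabilities are exact binomial enumerations at 100 per arm for the two-sided z-test without continuity correction.

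| f, standard vs aseptic | Observed rates | Rejection at 0.05 | Rejection at 0.025 |
|---|---|---|---|
| 5% vs 2% | 33.5% vs 31.4% | 6.2% | 3.3% |
| 10% vs 5% | 37.0% vs 33.5% | 8.1% | 4.5% |
| 10% vs 2% | 37.0% vs 31.4% | 13.3% | 8.1% |
| 10% vs 0% | 37.0% vs 30.0% | 18.3% | 11.7% |

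With a continuity correction the last row is 14.3% and 8.9%. The rates rise when true infection is rarer: at a true rate of 10%, 10% vs 5% rejects 13.8% of the time at 0.05 (uncorrected test).

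**The case against.** Counting empirically treated cases is a defensible choice. It captures infections treated elsewhere without a culture, and reviewing them may discard some real ones. The laboratory-confirmation sentence governs positive urine analyses and the treatment-only rule governs women without laboratory data, so the two can be read as separate routes. Emergency department cases receive some assessment. A woman treated by study staff, with no outside charted diagnosis, might still fall under the two-provider review. No section says who prescribes, and an emergency department prescriber may not know the arm. All of this stands. It does not supply masking, or a review criterion that antibiotic-only cases could meet.

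Three stronger readings are tempting, and the documents do not support them.

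- **A false-positive study dip automatically becomes a confirmed event.** A positive dip is listed as laboratory data suggesting infection, so the treatment-only sentence does not literally cover it, and a positive urine analysis must be laboratory-confirmed. What remains is an unanswered classification question.
- **Prescribing becomes the endpoint.** It is one route beside culture, chart diagnosis and provider review, and its share is unknown.
- **The dipstick risk statement contradicts the treatment statement in section IV.e.** The latter reads "Participation in this study will not have any influence on" current treatment. It is general risk wording, and reconciling the two would change no result.

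**Conclusion.** The concern holds in a limited form. Antibiotic-only cases are primary events, the plan describes no arm-masked review of them, and the existing review does not fit them. The classification of a woman treated on a dip that is not confirmed is also open.

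The size is unknown. An equal share of 5% to 15% costs 0.07 to 0.20 of power (0.840 to 0.774 or 0.637). Unequal shares inflate the false-positive rate by an amount that depends wholly on the assumed split. Mild splits do little (5% vs 2%: 6.2% at a nominal 5%, or 3.3% at a nominal 2.5%). The 18% figure needs 10% against none, an uncorrected test and no Bonferroni adjustment, so it is an upper illustration and not an expectation. Knowledge of the arm among prescribers is inferred from who inserts the catheter, the visible sleeve, the operation note and the silence on masking. The assumed direction, more treatment in the standard arm, is also a premise.

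The change should be made: it is cheap and affects what the trial can conclude.

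**What to change.** 1. In section VI, pre-specify culture-confirmed UTI (more than 10^5 CFU/mL, the plan's own threshold) as a parallel analysis with the same test, reported beside the composite. Report antibiotic-only events by arm. State that a difference confined to those events will be described as a difference in prescribing.
2. In section IV.a, replace automatic inclusion with referral. Antibiotic-only cases, and cases treated on a positive dip with negative confirmation, go to the existing two-provider review with the arm removed from the materials, including the operation note. Give the reviewers endpoint criteria that can be applied without a culture.

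The cost is some protocol and SAP wording, preparation of masked materials and a few more cases to review. The downside is that some true infections treated empirically may be ruled non-cases. Prescribing is still captured, because post-surgery antibiotic use is already a secondary outcome.

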Additional secondary outcomes to be evaluated will include patient discomfort with catheter, tolerability of catheter, length of hospital stay, and number of post-operative evaluations required. A cost-analysis will be performed as a secondary endpoint based on this cost factors (length of hospital stay, readmission, additional clinic/ED visits, antibiotic costs). Costs of hospital days, clinic visits, other appointments, and antibiotics will be standardized for evaluation based on literature for cost analysis in gynecologic oncology literature.

b. Target population. Women undergoing extended surgery lasting >1 hour and requiring urinary catheter will be eligible for enrollment. All patients will have surgery performed by one of the trained Gynecologic Oncologists at the University of Colorado Hospital.

Inclusion criteria will include:

- 1) women 18-89 years of age
- 2) admitted for surgery lasting >1 hour and requiring urinary catheter,
- 3) have normal urine analysis within 24 hours pre-surgery, and
- 4) able to provide informed consent.

Women with dialysis, chronic urinary infection, and current infection will not be eligible to participate. Women who are pregnant or breast feeding will not be included in the study. Men will not be included because of their lower incidence of UTIs compared to our female population.

The null hypothesis is that there will be no difference in UTI rates between the standard of care catheter placement and the sterile protocol placement. If we use the current rates of UTI after catheter placement described above at 40%, we would need to enroll 100 patients per arm (total 200) to see a 50% reduction in UTI rates in the intervention group with an alpha of 0.05 and a power of 0.84. The Gynecologic Oncology services averages around 5 surgical patients who would be eligible for this study per week. We anticipate needing between 10-12 months to complete enrollment.

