Participants will conduct the following study visits over 2 weeks. All costs associated with routine standard of care procedures for catheter insertions and diagnosing and treatment of a UTI will be the responsibility of the patient and/or their insurance provider. All costs associated with procedures conducted for research only will be paid for by the research study.

- **Visit 1 Screening and Enrollment:** Potential participants will be screened and consented for study up to 30 days prior to their surgical procedure. Inclusion/Exclusion criteria will be reviewed at the time of consent and baseline data including physical exam, health history, clinical diagnosis and concomitant medications will be collected following consent. A urine sample will be collected and analyzed 0-24 hours prior to procedure.
- **Visit 2 Randomization and Catheter Insertion:** Participants will be randomized to either the SOC catheter protocol or catheter insertion including Betadine on the day of procedure. Standard protocol will be followed for catheter preparation and insertion. Any adverse events following insertion will be recorded. Pre-operative antibiotics will also be recorded.
- **Visit 3, 24-hour post-op:** Patients will be assessed at 24 hours post-op in-patient. A urine sample will be collected and analyzed. Any positive urine analysis will be further analyzed and confirmed by the UCH laboratory per SOC procedures. Patients will be assessed for symptomatic signs of UTI and review of AEs following procedure.

- **Visit 4; 2-week post op:** Patients will be assessed 2-weeks post-op at their SOC post-op clinic visit. A urine sample will be collected and analyzed. Any positive urine analysis will be further analyzed and confirmed by the UCH laboratory per SOC procedures. A physical exam will also be collected. Patients will be assessed for symptomatic signs of UTI and review of AEs and ED visits since the last visit. Data including hospital stay, readmission, and antibiotic use will be collected. Patient satisfaction with catheter procedure will also be collected. Patient will be finished with study following visit 4.

e. Description, risks, and justification of procedures and data collection tools:

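### The abnormal-dip rule requires positive leukocyte esterase, so read literally a nitrite-only dip passes the entry screen and triggers no protocol culture at follow-up

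*Combined protocol and SAP*

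**What the plan says.** All references are to the combined protocol and SAP.

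- **The dip rule (IV.a, Performance Measurement).** "Results of +leukocyte esterase +/- nitrites will be considered abnormal". The list of laboratory data suggesting infection, earlier in the same section, has the same structure: "UA with +leukocyte esterase +/- nitrates" (printed there as nitrates).
- **Entry (IV.b, inclusion criterion 3).** A woman must "have normal urine analysis within 24 hours pre-surgery". Normal is not defined. IV.e gives the purpose of this test: "Pre-operative/pre-randomization allows us to exclude patients who may have underlying UTI prior to initiation of the study". No culture is planned at entry.
- **Follow-up (IV.d, Visits 3 and 4).** "Any positive urine analysis will be further analyzed and confirmed by the UCH laboratory per SOC procedures". IV.a agrees: "All positive UA test will be confirmed by laboratory analysis for final diagnosis". IV.e describes culture as a means of confirming UTI. No section orders culture of every follow-up sample.
- **Endpoint (IV.a).** "Asymptomatic bacteriuria will be considered a UTI for this study", defined as more than 10^5 CFU/mL on culture.
- **Other routes to an event (IV.a).** Symptoms are assessed at follow-up, ED reports are obtained and reviewed, antibiotic treatment for UTI counts without laboratory data, and a chart diagnosis is accepted.

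**The concern.** One rule does two jobs: it decides who may be randomised and whose follow-up urine is cultured. Because it makes esterase a necessary condition, a nitrite-only dip falls outside it both times.

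At follow-up, asymptomatic bacteriuria can be established only by culture, and for a woman with no symptoms the dip is the protocol's only planned route to culture. A nitrite-only dip closes that route, and any bacteriuria she has goes uncounted.

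At entry, the same result lets her through a screen intended to exclude underlying UTI. If she already has bacteriuria and her esterase later turns positive, culture would record it as a post-catheter event. Catheter technique cannot prevent an infection that was already there, so such cases would pull the comparison towards no difference. Randomisation balances them between arms on average but does not remove the dilution.

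**Working it through.** **1. What the text does with each dip result, read literally**

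| Dip result | Under the IV.a rule | Entry (criterion 3) | Visits 3 and 4 |
|---|---|---|---|
| Esterase +, nitrite + | abnormal | fails | laboratory confirmation |
| Esterase +, nitrite − | abnormal | fails | laboratory confirmation |
| Esterase −, nitrite + | not listed as abnormal | passes | no culture triggered |
| Esterase −, nitrite − | not listed as abnormal | passes | no culture triggered |

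The third row is the point at issue. The fourth row is a limit of any dip-triggered design, and changing the rule does not alter it.

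**2. The plan's own figure**

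Inputs from IV.b: 40% v 20%, alpha 0.05, power 0.84, 100 per arm. The plan does not state sidedness; two-sided is assumed.

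Uncorrected size: n0 = [1.960·√(2·0.30·0.70) + 0.9945·√(0.40·0.60 + 0.20·0.80)]² / 0.20² = (1.270 + 0.629)² / 0.04 = 90.2.

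With continuity correction: n = (n0/4)·[1 + √(1 + 4/(n0·0.20))]² = 22.54 × 4.43 = 99.9, so 100 per arm. The stated size reproduces.

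The power figures below use exact binomial enumeration at 100 per arm. The test is the pooled z with continuity correction, z = (|x1 − x2|/100 − 1/100) / √(2·p̄(1 − p̄)/100), rejecting at 1.96. At 40% v 20% this gives 0.844. Alpha is kept at 0.05 to match the sample-size statement.

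**3. Events lost through nitrite-only dips**

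Assumptions, none given in the documents: half of events are asymptomatic; a share s of those is nitrite-only; all of these are missed, equally in both arms. Observed rate = true rate × (1 − 0.5·s).

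| s | Observed rates | Events lost per 100 (control, intervention) | Power |
|---|---|---|---|
| 0 | 40.0% v 20.0% | 0, 0 | 0.844 |
| 2% | 39.6% v 19.8% | 0.4, 0.2 | 0.839 |
| 5% | 39.0% v 19.5% | 1.0, 0.5 | 0.830 |

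**4. Scale of the wider, separate gap**

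If all dip-normal bacteriuria is counted, including samples negative on both markers, shares of 10%, 20%, 30% and 50% of asymptomatic cases give 38/19, 36/18, 34/17 and 30/15%. Power is then 0.815, 0.783, 0.747 and 0.668. A change to the nitrite rule recovers only the nitrite-only part of these losses.

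**5. Bacteriuria present at entry**

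Suppose a share q enters with undetected bacteriuria that is later counted as an event, and the remainder keep the 40% v 20% risk. The rates are q + (1 − q)·0.40 and q + (1 − q)·0.20.

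- q = 5%: 43.0% v 24.0%, ratio 0.56, power 0.775.
- q = 8%: 44.8% v 26.4%, ratio 0.59, power 0.732.

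If the control rate is instead held at 40% and pre-existing cases replace new ones, 5 points give 40% v 22.5% and power 0.719; 8 points give 40% v 24% and power 0.628. These q values are illustrative. For the nitrite-only rule alone, q counts only women who are esterase-negative and nitrite-positive at entry and are later detected. The documents give no such share.

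**The case against.** The strongest reply is that IV.a says certain results are abnormal without saying that only those are. Normal and positive are undefined, so staff could treat a nitrite-positive dip as positive; current infection and chronic urinary infection are separate exclusions in IV.b. This is fair as far as it goes. But the written rule is the only one that staff have, and if they read it differently, eligibility and endpoint detection vary by reader. The separate exclusions do not find silent bacteriuria; IV.e assigns that job to the dip.

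A second reply is that dip-triggered culture is a workable design, applied alike in both arms, and that the sample size is correct. That also stands. Under-detection that is equal in both arms costs some power and does not favour either arm.

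Four stronger readings are tempting and are not supported:

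- *Nitrite-only women are never cultured.* Symptoms, ED review and ordinary clinical care can still lead to culture, and antibiotic treatment or a chart diagnosis can make the woman a case without it. The gap is in protocol-triggered culture and mainly concerns women without symptoms.
- *The protocol contradicts itself because it treats nitrite alone as a sign of infection.* Both statements in IV.a require esterase, and they agree.
- *The rule costs power down to about 0.67.* That figure needs half of asymptomatic cases to be dip-normal, which includes samples negative on both markers.
- *Observed rates must fall below the planned 40%.* The discussion of discomforts under Anticipated Risks says that the figure covers symptomatic and asymptomatic UTI, but no section says how it was ascertained. If it came from similar dip-triggered testing, there is no shortfall from this source.

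**Conclusion.** The concern holds as a gap in the dip definition. Read literally, nitrite-only dips pass inclusion criterion 3 and trigger no protocol culture at Visits 3 and 4. This sits poorly with an endpoint that counts culture-defined asymptomatic bacteriuria and with an entry dip meant to exclude underlying UTI.

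The effect is probably small, and its true size cannot be derived from the documents. Under the stated assumptions for missed events, power falls by about 0.5 to 1.4 percentage points. Dilution from nitrite-only bacteriuria at entry would come on top of this, but its share is unknown. Larger losses would come from bacteriuria negative on both markers, which is a separate matter. The change is still worth making because it is nearly free and settles who is eligible and who is cultured.

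**What to change.** In IV.a, define an abnormal dip, stated to mean the same as a positive dip, as leukocyte esterase positive **or** nitrite positive. Use that single definition for inclusion criterion 3 in IV.b and as the trigger for confirmatory culture at Visits 3 and 4 in IV.d. Print nitrites consistently. In the report, describe the asymptomatic component of the endpoint as dip-screened, culture-confirmed bacteriuria, so that readers know samples negative on both markers were not routinely cultured.

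The cost is a short edit to the protocol and CRF, with no new sample. The downside is a few more screen failures and a few more confirmatory cultures.

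Culturing every follow-up sample whatever the dip shows (at most 200 × 2 = 400 tests) would also find bacteriuria negative on both markers. It is a separate and costlier choice and is not part of this fix.
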